**Table 27 (Cont.) – Biochemistry – Safety population**

	Total (n=xx)				
	Screening	Baseline	Visit xx	End of study treatment	End of study
LDH, n (%)					
Normal					
Abnormal, clinically irrelevant					
Abnormal, clinically relevant					
Total					
Baseline versus current visit					
Normal - Normal	-	-	-	-	-
Normal - Abnormal, clinically irrelevant	-	-	-	-	-
Normal - Abnormal, clinically relevant	-	-	-	-	-
Abnormal, clinically irrelevant - Normal	-	-	-	-	-
Abnormal, clinically irrelevant - Abnormal, clinically irrelevant	-	-	-	-	-
Abnormal, clinically irrelevant - Abnormal, clinically relevant	-	-	-	-	-
Abnormal, clinically relevant - Normal	-	-	-	-	-
Abnormal, clinically relevant - Abnormal, clinically relevant	-	-	-	-	-
Abnormal, clinically relevant - Abnormal, clinically irrelevant	-	-	-	-	-
Alkaline phosphatase, n (%)					
Normal					
Abnormal, clinically irrelevant					
Abnormal, clinically relevant					
Total					
Baseline versus current visit					
Normal - Normal	-	-	-	-	-
Normal - Abnormal, clinically irrelevant	-	-	-	-	-
Normal - Abnormal, clinically relevant	-	-	-	-	-
Abnormal, clinically irrelevant - Normal	-	-	-	-	-
Abnormal, clinically irrelevant - Abnormal, clinically irrelevant	-	-	-	-	-
Abnormal, clinically irrelevant - Abnormal, clinically relevant	-	-	-	-	-
Abnormal, clinically relevant - Normal	-	-	-	-	-
Abnormal, clinically relevant - Abnormal, clinically relevant	-	-	-	-	-
Abnormal, clinically relevant - Abnormal, clinically irrelevant	-	-	-	-	-

**Table 27 (Cont.) – Biochemistry – Safety population**

	Total (n=xx)				
	Screening	Baseline	Visit xx	End of study treatment	End of study
Total bilirubin, n (%)					
Normal					
Abnormal, clinically irrelevant					
Abnormal, clinically relevant					
Total					
Baseline versus current visit					
Normal - Normal	-	-	-	-	-
Normal - Abnormal, clinically irrelevant	-	-	-	-	-
Normal - Abnormal, clinically relevant	-	-	-	-	-
Abnormal, clinically irrelevant - Normal	-	-	-	-	-
Abnormal, clinically irrelevant - Abnormal, clinically irrelevant	-	-	-	-	-
Abnormal, clinically irrelevant - Abnormal, clinically relevant	-	-	-	-	-
Abnormal, clinically relevant - Normal	-	-	-	-	-
Abnormal, clinically relevant - Abnormal, clinically relevant	-	-	-	-	-
Abnormal, clinically relevant - Abnormal, clinically irrelevant	-	-	-	-	-

**Table 28 – Adverse events and serious adverse events – Safety population**

	Total (n=xx)
Patients with at least one adverse event, n (%)a)	
No	
Yes	
Total	
Patients with at least one serious adverse event, n (%)a)	
Yes	
No	
Total	
Patients with at least one adverse event of special interest, n (%)a)	
Stevens-Johnson Syndrom	
Interstitial Lung Disease	
Grade of adverse events, n (%)b)	
Grade 1	
Grade 2	
Grade 3	
Grade 4	
Grade 5	
Total	
Severity of adverse events, n (%)b)	
Mild	
Moderate	
Severe	
Life threatening or disabling	
Death related	
Total	
Relationship of study drug, n (%)b)	
Unrelated	
Remote relation	
Possible relation	
Probable relation	
Total	
Action taken for adverse event, n (%)b)	
Dose increased	
Dose not changed	
Dose reduced	
Drug interrupted	
Drug withdrawn	
Not applicable	
Unknown	
Serious adverse events, n (%)b)	
Yes	
No	
Outcome, n (%)b)	
Not recovered / Not resolve	
Recovering / Resolving	
Recovered / Resolved	
Recovered / Resolved with sequelae	
Fatal	
Unknown	

a) Percentage calculated within the total number of patients of safety population (n=xx).

b) Percentage calculated within the total number of adverse events reported by safety population (n=xxx).

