8.2.4 Safety Data Analysis

The safety analysis population will include all subjects who receive at least one dose and had a safety assessment performed at baseline. All safety parameters will be summarized using descriptive measures and presented in tables based on this safety population.

Adverse event data will be presented in frequency tables (overall and by intensity) by body system. In tables showing the overall incidence of adverse events, subjects who experienced the same event on more than one occasion are counted only once in the calculation of the event frequency.

For selected events of particular interest summary tables will be presented for time to first onset of the event and for the total number of episodes. Every occurrence of an event in any subject will be counted in the total number of episodes but successive reports of an identical event in the same phase (treatment, follow-up) will be combined (concatenated) into a one episode if the end date of the earlier event was the same as the start date of the later event, or if the end date of the earlier event was missing.

All AEs and laboratory variables will be assessed according to the NCI CTC-AE version 4.0 grading system.

Laboratory values will be listed with flagging of values outside of normal range, and summarized in shift from baseline tables.

Information on the study drug will be summarized by duration, starting dose, dose per day and cumulative dose using descriptive statistics.

All AEs and laboratory variables will be assessed according to the NCI CTC-AE version 4.0 grading system.

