### **5.3.10.4 Laboratory data**

Laboratory assessment will be carried out at the screening visit and all visits during the treatment period. For the following laboratory parameters:

- 1) Hematology (hemoglobin, leucocytes, neutrophils, platelets),
- 2) Coagulation (prothrombin time, activated partial thromboplastin (aPTT), international normalized ratio (INR – only at the screening visit) and
- 3) Biochemistry (urea, glucose, AST, ALT, creatinine clearance (if indicated), serum creatinine, calcium, sodium, potassium, chloride, LDH, alkaline phosphatase, total bilirubin)

the percentage of patients with abnormal clinically relevant values will be assessed.

Laboratory will be summarized in shift from baseline tables.

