### **5.3.10.5 Adverse events**

Adverse event (AE) data will be presented in frequency tables (overall, by grade (1, 2, 3, 4, or 5), by severity (mild, moderate, severe, life threatening or disabling or death related), by relationship (unrelated, remote relation, possible relation or probable relation) and by action taken (dose changed, interrupted, withdrawal or none). In tables showing the incidence of adverse events, subjects who experienced the same event on more than one occasion are counted only once in the calculation of the event frequency.

For selected events of particular interest, such as Stevens-Johnson syndrome and interstitial lung disease, summary tables will be presented for time to first onset of the event and for the total number of episodes. Every occurrence of an event in any subject will be counted in the total number of episodes but successive reports of an identical event in the same phase (treatment, follow-up) will be combined (concatenated) into a one episode if the end date of the earlier event was the same as the start date of the later event, or if the end date of the earlier event was missing.

A listing of adverse events by patient, whose adverse events led to withdrawal of study treatment or to dose modification will be done. In case of deaths, a brief narrative describing each death will be done.

All AEs and laboratory variables will be assessed according to the NCI CTC-AE version 4.0 grading system.

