STATISTICAL CONSIDERATIONS  - STATISTICAL METHODS	
Efficacy Analyses:
 
The primary and secondary efficacy analyses will be performed on the intent-to-treat population, defined as all subjects who are enrolled to the treatment phase of the study, regardless if they completed treatment. For ORR 95% confidence interval will be estimated. PFS and OS will be estimated and presented as median time to PFS and OS through Kaplan-Meier method. 95% confidence intervals will be estimated for this parameters. EGFR expression will be presented as a percentage and 95% confidence intervals will be estimated for this value.

- SAMPLE SIZE CONSIDERATION
	
Safety Analyses:
 
All safety parameters will be summarized and presented in tables based on the safety population.
 
AE data will be presented in standard frequency tables (overall and by intensity) by body system. All AEs and laboratory variables will be assessed according to the NCI CTC-AE version 4.0 grading system.
 
The sample size was calculated based on the primary variable of the study, objective response rate. Since this proportion is unknown an exploratory sample size of 30 patients was considered to evaluate primary endpoint. This sample size will allow estimating ORR with a margin of error of approximately <math>\pm 17.5\%</math>, for a 95% confidence interval.
 
Furthermore, approximately 2000 new cases of stage IIIB and IV NSCLC are diagnosed per year in Portugal and, based on published data, expected prevalence of EGFR mutation is approximately 10%. With a 95% confidence interval, it was calculated that at least 420 patients will have to be enrolled to be tested to achieve 30 positive cases for the exploratory sample size analysis.

------------------------------------	---

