**Table 29 – Incidence of adverse events – Safety population**

	Total (n=xx)
Incidence of adverse events, n (%)	
Body system 1	
Xxxxx	
Xxxxx	
Xxxxx	
Body system 2	
Xxxxx	
Xxxxx	
Xxxxx	

a) Percentage calculated for total of patients of patients of the safety population (n=xx).

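### No planned SAP table shows adverse-event severity by body system, and Table 28's grade percentages do not determine how many patients had severe toxicity

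*SAP*

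**What the plan says.** Protocol 8.2.4 sets the requirement: "Adverse event data will be presented in frequency tables (overall and by intensity) by body system". SAP Appendix 1 repeats it: "AE data will be presented in standard frequency tables (overall and by intensity) by body system". The body of the SAP, in 5.3.10.5, promises grade and severity but does not mention body system: "Adverse event (AE) data will be presented in frequency tables (overall, by grade (1, 2, 3, 4, or 5), by severity". The same section says that incidence tables count a subject once per event, but gives no rule for which grade to keep when an event recurs.

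The shells in SAP Appendix 6 are arranged as follows:

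- **Table 28** has grade and severity rows, not split by body system or term. Footnote b gives their denominator: "Percentage calculated within the total number of adverse events reported by safety population (n=xxx". Its patient-level rows cover only any AE, any serious AE, Stevens-Johnson syndrome and interstitial lung disease.
- **Tables 29 to 32** are patient-level by body system and term, with the footnote "Percentage calculated for total of patients of patients of the safety population (n=xx". They have a single Total column and no grade.
- **Tables 33 to 36** are by body system and term with event denominators, also without grade.
- **Listing 4** gives patient, event and grade line by line.

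For the interim, Protocol 3.3 says safety will be evaluated by type of event, frequency and severity. SAP 6.12 limits the interim AE output to Tables 29 to 34, 36 and 39.

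On laboratory data, SAP 5.3.10.5 states: "All AEs and laboratory variables will be assessed according to the NCI CTC-AE version 4.0 grading system". Protocol 8.2.4 says the same about grading and describes the display: "Laboratory values will be listed with flagging of values outside of normal range, and summarized in shift from baseline tables".

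**The concern.** The safety profile is a secondary objective. Protocol 6.1 calls diarrhoea and skin rash the major side effects, and toxicity management in Table 4 of the protocol depends on grade. A reader of the final report will want to know what share of patients had Grade 3 or higher rash, diarrhoea or any other event. No planned table answers that. The only tabulated severity figure has all reported events as its denominator, so it depends on how many mild events were recorded and on how severe events are spread over patients.

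**Working it through.** No stated sample size, power or event count is in dispute, so there is no plan figure to reproduce. The check compares requirement with shell, then asks what Table 28 can tell a reader.

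**Requirement against shell**

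| Needed | Table 28 | Tables 29-32 | Tables 33-36 |
|---|---|---|---|
| Intensity or grade | yes | no | no |
| By body system | no | yes | yes |
| Patient denominator for the event breakdown | no | yes | no |

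No table has both of the first two rows, which are what Protocol 8.2.4 and SAP Appendix 1 ask for. Protocol 7.1.3 explains severity as the intensity of an event, including by CTCAE grade, so grade is a fair reading of intensity.

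**Interim.** The SAP 6.12 list includes Tables 29 and 31 but not Table 28. Since Table 28 is the only AE table with grade or severity, none of the listed interim tables shows either.

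**What an event share implies for patients.** Let n be the patients treated, A all reported AEs, and G the AEs of Grade 3 or higher. Table 28 gives G/A. The number of patients with at least one such event can be as low as 1 (all in one patient) or as high as the smaller of G and n (one per patient). The patient share therefore lies between 1/n and min(G, n)/n.

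Inputs: n = 30 is the planned sample size (SAP 5.1). G and A are assumptions, because the documents give no expected AE counts. Intervals are exact (Clopper-Pearson) 95%.

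- G = 15, A = 150: Table 28 shows 15/150 = 10%. The patient share runs from 1/30 = 3.3% (0.1 to 17.2%) to 15/30 = 50.0% (31.3 to 68.7%).
- G = 10, A = 200: Table 28 shows 10/200 = 5%. The patient share runs from 1/30 = 3.3% to 10/30 = 33.3% (17.3 to 52.8%).

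In both examples the Table 28 figure lies inside the possible range, so it can be above or below the patient rate.

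**The case against.** The strongest reply is that the information is planned even if the summary is not. Listing 4 shows grade for every AE by patient, and with about 30 patients a reader could count. Serious AEs are tabulated per patient by body system in Table 30. For events graded with protocol Table 5, Grade 4 and 5 events must be reported as serious. That narrows the gap mainly to non-serious Grade 3 events. It does not close it: a listing is not the frequency table the protocol asks for, and Protocol 7.1.3 itself says that severe and serious are different things.

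Two further replies have force. Protocol 8.2.4 sets no denominator for intensity tables, so worst grade per patient is a recommended way to fill the gap and not itself a protocol requirement. And the detailed interim list in Protocol 8.2.7 does not name severity, so SAP 6.12 follows that section while missing what Protocol 3.3 promises.

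A reader might also infer more than the documents support:

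- **That Table 28 understates patient risk.** It may, if severe events are spread one per patient. If they cluster in a few patients it overstates.
- **That the patient share could not be stated at all.** It could be derived from the data behind Listing 4; no table plans it.
- **That liver-test changes are a main toxicity left ungraded.** Protocol 1.2 describes them as less frequent with erlotinib alone, which is this trial's regimen.
- **That the laboratory tables breach the protocol.** SAP 5.3.10.4 summarises by clinical relevance ("the percentage of patients with abnormal clinically relevant values will be assessed"), and Tables 25 to 27 show shifts between normal, clinically irrelevant and clinically relevant. Protocol 8.2.4 asks for shift tables and says variables are assessed by CTCAE grade, but does not specify a graded shift table. Protocol 7.1.6 also sends abnormal results that cause symptoms or a treatment change into the AE data, including results from tests outside the protocol.

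**Conclusion.** The point holds for adverse events. The shells conflict with Protocol 8.2.4 and with the SAP's own synopsis, and the interim output conflicts with Protocol 3.3. The consequence is a missing summary for a secondary objective, not lost data, and the primary endpoint is untouched. The size can only be illustrated: under the assumed 15 Grade 3 or higher events among 150 AEs, a reported 10% is compatible with 3.3% to 50% of 30 patients. That range rests on assumed counts and on the extremes of clustering, so it shows that Table 28 is uninformative about patients and predicts no result. The laboratory side supports an optional improvement only.

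**What to change.** Add columns to Tables 29 and 31 for worst CTCAE grade per patient (any grade, Grade 3-4, Grade 5), by body system and term. Use the safety population as denominator and count each patient once per term. State in SAP 5.3.10.5 that a patient with repeated occurrences of an event is counted at the worst grade. Because SAP 6.12 already lists both tables, this also supplies severity for the interim without changing that list. AE grade is already collected for Listing 4, so the cost is a short SAP edit, table programming and somewhat longer tables.

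Optionally, since both documents say laboratory variables are assessed by CTCAE grade, add baseline grade against worst post-baseline grade for gradable parameters. This should be limited to parameters whose numeric values and local reference ranges are in the database. Testing is done at local laboratories (Protocol 5.4), and the documents do not show that unscheduled numeric values reach the analysis database, so availability needs checking before this is promised.

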**Table 29 – Incidence of adverse events – Safety population**

	Total (n=xx)
Incidence of adverse events, n (%)	
Body system 1	
Xxxxx	
Xxxxx	
Xxxxx	
Body system 2	
Xxxxx	
Xxxxx	
Xxxxx	

a) Percentage calculated for total of patients of patients of the safety population (n=xx).

**Table 30 – Incidence of serious adverse events – Safety population**

	Total (n=xx)
Incidence of serious adverse events, n (%)	
Body system 1	
Xxxxx	
Xxxxx	
Xxxxx	
Body system 2	
Xxxxx	
Xxxxx	
Xxxxx	

a) Percentage calculated for total of patients of patients of the safety population (n=xx).

**Table 31** – Incidence of adverse events with remote, possible or probable relationship with study drug – Safety population

	Total (n=xx)
Incidence of adverse events with remote, possible or probable relationship with study drug, n (%)	
Body system 1	
Xxxxx	
Xxxxx	
Xxxxx	
Body system 2	
Xxxxx	
Xxxxx	
Xxxxx	

a) Percentage calculated for total of patients of patients of the safety population (n=xx).

**Table 32** – Incidence of serious adverse events with remote, possible or probable relationship with study drug – Safety population

	Total (n=xx)
Incidence of serious adverse events with remote, possible or probable relationship with study drug, n (%)	
Body system 1	
Xxxxx	
Xxxxx	
Xxxxx	
Body system 2	
Xxxxx	
Xxxxx	
Xxxxx	

a) Percentage calculated for total of patients of patients of the safety population (n=xx).

**Table 33 – Adverse events – Safety population**

	Total (n=xx)
Adverse events, n (%)	
Body system 1	
Xxxxx	
Xxxxx	
Xxxxx	
Body system 2	
Xxxxx	
Xxxxx	
Xxxxx	

Percentage calculated within the total number of adverse events reported by safety population (n=xxxx).

**Table 34 – Serious adverse events – Safety population**

	Total (n=xx)
Serious adverse events, n (%)	
Body system 1	
Xxxx	
Xxxx	
Xxxx	
Body system 2	
Xxxx	

Percentage calculated within the total number of serious adverse events reported by safety population (n=xxxx).

**Table 35** – Adverse events with remote, possible or probable relationship with study drug – Safety population

	Total (n=xx)
Adverse events with remote, possible or probable relationship with study drug, n (%)	
Body system 1	
Xxxxx	
Xxxxx	
Xxxxx	
Body system 2	
Xxxxx	
Xxxxx	
Xxxxx	

Percentage calculated within the total number of adverse events with remote, possible or probable relationship with study drug reported by safety population (n=xxxx).

**Table 36** – Serious adverse events with remote, possible or probable relationship with study drug – Safety population

	Total (n=xx)
Serious adverse events with remote, possible or probable relationship with study drug, n (%)	
Body system 1	
Xxxx	
Xxxx	
Xxxx	
Body system 2	
Xxxx	
Xxxx	
Xxxx	

Percentage calculated within the total number of serious adverse events with remote, possible or probable relationship with study drug reported by safety population (n=xxxx).

**Table 37 – Adverse events of special interest: Interstitial lung disease – Safety population**

	Total (n=xx)
Time to first onset, n (%)	
N	
Mean	
Median	
Standard Deviation	
Minimum	
Maximum	
Total number of episodes, n (%)	
N	
Mean	
Median	
Standard Deviation	
Minimum	
Maximum	

**Table 38 – Adverse events of special interest: Stevens-Johnson syndrome – Safety population**

	Total (n=xx)
Time to first onset, n (%)	
N	
Mean	
Median	
Standard Deviation	
Minimum	
Maximum	
Total number of episodes, n (%)	
N	
Mean	
Median	
Standard Deviation	
Minimum	
Maximum	

**Table 39 – Subsequent therapy for NSCLC – Safety population**

	Total (n=xx)
	Visit XX
Subsequent therapy, n (%)	
Yes	
No	
Total	
Therapeutic line, n (%)	
Second	
Third / Fourth	
Paliative Care	
Total	
Treatment	
Xxxx	

# Appendix 7: Listings

**Listing 1** – Co-morbidities – ITT population

Center	Patient	Co-morbidity	Grade	Severity	Start year

**Listing 2 – Abnormal findings in ECOG results – ITT population**

Center	Patient	Date	Location	Result	Description

**Listing 3 – Concomitant medication – ITT population**

Center	Patient	Treatment name	Indication	Dose	Unit	Route	Frequency	First taken	Ongoing	Last taken
--------	---------	----------------	------------	------	------	-------	-----------	-------------	---------	------------

**Listing 4 – Adverse events – Safety population**

Center	Patient	Adverse event	Grade	Severity	Relationship	Outcome	Action taken	Seriousness	Date started	Date ended	Duration of AE	AE related Concomitant Medication
